## 4 PLANNED ANALYSES

### 4.1 Preliminary Analyses and Missing Data

Analyses will use all available data (intent-to-treat) [93]. If dropout is related to other variables, they will be included as predictors. Baseline between-group differences on demographic variables will be examined. These tests will not be used to select covariates in the primary intention-to-treat analysis [94-97]. Instead, covariates will be carefully selected at the conclusion of the trial—given the variations due to COVID-19 and the CMHC context (see Discussion)—and the potential influences of baseline differences will be evaluated as moderators (approach to moderation described below). Analyses comparing TranS-C to UC-DT will evaluate change in outcomes from pre-treatment to post-treatment. Analyses comparing Adapted to Standard TranS-C will evaluate change in outcomes from pre-treatment to post-treatment and pre-treatment to 6FU (see Method and Discussion for more details).

Distributions will be evaluated to detect outliers, and we will ensure that assumptions of planned analyses are met. Covariates will include the patient variables for which we stratified (i.e., age and presence of psychosis or substance use). For all statistical models, counties will be entered as dummy variables rather than a level of analysis due to the relatively small number of clusters. The average intraclass correlation on provider and patient level outcomes will be reported. The Benjamini–Hochberg procedure [98] will be used to correct for multiple testing for confirmatory analyses on the primary outcomes (i.e., sleep disturbance and acceptability) [99].

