First, we did not collect data from leadership at our partner CMHCs. The primary reason was that these leaders have many demands on their time and already had generously collaborated with us on the design and implementation of the study. However, we recognize that leadership-level factors can meaningfully impact implementation outcomes [109]. Thus, exploring leadership perspectives on TranS-C will be an important direction for future research. Second, we considered additional assessment methods for sleep and circadian problems, such as a diagnostic interview (e.g., the Duke Structured Interview for Sleep Disorders; [63]) and polysomnography. However, even without these more intensive diagnostic tools, some patients reported difficulty with the length of assessments. Additionally, we were interested in recruiting patients with a broad range of symptom severity, which may have more ecological validity than a more restricted sample. That said, we acknowledge that there are certain outcomes that we will not be able to address due to this design choice (e.g., change in diagnostic status). Third, assessors are not blind to treatment condition at pre-treatment. To minimize burden on participants (e.g., reduce number of calls from team), assessors are in charge of the consent process, and therefore, they need to provide study-related information—such as number of assessments and treatment sessions—to the patients. At post-treatment and 6FU, we endeavor to keep the assessors blind but, as is common in clinical trials, there are ways that assessors may be able to infer treatment condition (e.g., slightly different assessment batteries). In rare instances, patients in the UC-DT condition ask assessors questions such as “when does treatment start?” or “when will I receive the workbook?” during the post-delay assessment. In such instances, the assessor may be able to ascertain that the patient has been assigned to the UC-DT condition. Assessors receive ongoing supervision and are thoroughly trained to deliver the surveys with integrity and minimal bias. Additionally, relative to interviews or clinical rating scales, the standardized surveys delivered by assessors are likely less vulnerable to bias (see Measures above). However, it is possible that assessor knowledge or hunches about patients’ condition may influence patient responses. Fourth, in the UC-DT condition, patients did not complete a 6FU assessment after the delay. This was a compromise made with CMCH partners, so that patients would not need to wait 7 to 8 months to receive treatment. Thus, analyses comparing TranS-C with UC-DT will evaluate outcomes from pre- to post-treatment, whereas analyses comparing Adapted versus Standard TranS-C can evaluate outcomes from pre- to post-treatment *and* pre- to 6FU. Depending on the outcomes from the trial, an important direction for future research will be testing the long-term effects of TranS-C relative to a control (e.g., UC-DT). Fifth, unforeseen challenges arose related to the COVID-19 pandemic and subsequent mandates in California (e.g., shelter-in-place). For some patients, sleep and circadian treatment became secondary to coping with other mental health ramifications of the pandemic (e.g., anxiety, isolation, grief) or even meeting basic needs of secure access to food and shelter [110]. Additionally, providers suddenly had more demands on their time, such as navigating the shift from in-person to virtual care—a shift that was also challenging for some patients. These changes had implications for the present study. For instance, we did not design the study to systematically evaluate potential differences in TranS-C delivery (i.e., in-person versus virtual versus phone). As another example, there was substantial turnover in providers and patients, leading to more discontinuity across treatment than anticipated. Sixth, some design choices were made to respect the expertise and preferences of our CMHC partners. For example, providers had the option to deliver TranS-C in a group or individual format. Even though this introduced variance into the study, it has been critical to the CMHCs, providers, and patients that we balance rigor with flexibility. We deliberated about whether to control for these variations necessitated by COVID-19 and the CMHC contexts. Ultimately, we decided against a prespecifying a comprehensive list of possible covariates, given the statistical drawbacks of controlling for many variables (e.g., [94-97]). At the conclusion of the trial, the sources of variation that resulted from the COVID-19 pandemic and needs/preferences of our community partners will be carefully considered as to whether they should be included as covariates.

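### Additional covariates for the primary models are left open until the trial ends, with no selection rule, no lock before outcomes are seen by arm, and no bar on post-randomization variables

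*Combined protocol and SAP*

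**What the plan says.** Section 4.1 settles part of the covariate set. County dummies go into every model, and "Covariates will include the patient variables for which we stratified" (age, psychosis, substance use). Tests of baseline imbalance are ruled out as a way of choosing covariates for the primary intention-to-treat analysis.

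Two routes stay open.

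- **Late selection.** Because of variation due to COVID-19 and the CMHC setting, "covariates will be carefully selected at the conclusion of the trial". The Discussion confirms the choice: "Ultimately, we decided against a prespecifying a comprehensive list of possible covariates". It adds that at the end "the sources of variation that resulted from the COVID-19 pandemic and needs/preferences of our community partners will be carefully considered" for inclusion. The variation it describes includes in-person, virtual or phone delivery, substantial provider and patient turnover, and the fact that "providers had the option to deliver TranS-C in a group or individual format".
- **Dropout.** "If dropout is related to other variables, they will be included as predictors". This is not limited to variables measured at baseline.

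The confirmatory tests are the treatment by time interactions at the 5% level (4.3 for sleep disturbance, 4.4 for acceptability). The equations there list time, treatment, their interaction and county. Neither shows how any other covariate enters, including the strata that 4.1 promises. No strata-and-county-only model is named as the confirmatory one.

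**The concern.** Two separate problems follow from leaving the additional set open.

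1. **Freedom of choice.** If several models are admissible and the choice comes after outcomes can be seen by arm, the nominal 5% level is not guaranteed. The plan contains nothing that would rule out a favorable choice: no rule, no blinded selection step, no lock date.
2. **Kind of variable.** Delivery mode, format and turnover come into being after randomization. Conditioning on a variable that the arm influences and that is also tied to prognosis biases the randomized comparison. Naming the variable in advance does not cure this. For Aim 1 there is a further difficulty: mode and format have no value for UC-DT patients before their post-delay assessment (3.4.3, 3.6.2), so they cannot be like-for-like covariates there.

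At stake are the tests on the two primary outcomes, sleep disturbance and acceptability.

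**Working it through.** **Inputs from the plan.** Section 3.8 uses a two-sided alpha of 0.05. It plans 240 + 240 = 480 patients and 80 providers before attrition. The targets reproduce: 480 × 1.2 = 576 and 80 × 1.2 = 96. The plan gives no figure for the covariate choice itself, so the reference is the nominal 5%.

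**Assumed inputs.** The documents do not give the number of optional covariates, the share of change they explain, or how far the arm shifts a post-randomization covariate. All simulations have no true treatment effect and 480 patients randomized 1:1 individually, without county clustering.

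**Step 1: late choice among baseline-type covariates, acting on change.** The change score is regressed on treatment plus every subset of the optional covariates, and the smallest p-value is kept. This is a deliberate worst case.

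| Optional covariates | Share of change explained | Type I error, full set fixed in advance | Type I error, most favorable subset |
|---|---|---|---|
| 3 | 10% / 20% / 30% | 4.7% / 5.3% / 5.1% | 7.4% / 10.2% / 11.1% |
| 5 | 10% / 20% / 30% | 5.3% / 4.8% / 5.3% | 9.6% / 11.9% / 15.0% |

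**Step 2: form of entry in a two-wave model.** This uses three optional covariates, 1,500 runs per row, unit variances and correlation 0.5. The change variance is 2 − 2 × 0.5 = 1. The covariates add 0.20 to it, so they explain 0.20/1.20 = 17% of change. Post-treatment data are missing completely at random.

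| Entry | Missing | No optional covariate | Most favorable subset |
|---|---|---|---|
| Main effect | 0% | 5.7% | 6.0% |
| By time | 0% | 4.9% | 8.9% |
| Main effect | 20% | 6.7% | 7.1% |
| By time | 20% | 6.6% | 10.1% |

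A fixed working correlation was used, so the null rate itself runs from 5% to 7%; compare within rows. As a main effect with complete data, the covariates leave the treatment by time estimate unchanged. With 20% missing, they move it by about 0.003 SD on average.

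**Step 3: one post-randomization covariate.** Let Z = U + s × T, where T is the arm and U is prognosis. U explains a share R² of change, and the arm has no effect. Adjusting change for Z biases the treatment effect by s × √R² in absolute size.

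- s = 0.2, R² = 0.05: 0.2 × √0.05 = 0.045 SD (simulated 0.044; 8% rejections).
- s = 0.5, R² = 0.20: 0.5 × √0.20 = 0.224 SD (simulated 0.223; 75% rejections).

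In the two-wave model with s = 0.5 and a coefficient of √0.10, entry by time gave 42% rejections with complete data and 37% with 20% missing. As a main effect it gave 6.1% and 5.7%. The bias formula does not depend on N. The rejection rates do, and they do not carry over to 80 providers.

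**Step 4: can county enter by time?** Adapted versus Standard is constant within county. With 10 counties and two waves there are 20 county-by-wave cells. Intercept, time, 9 county dummies and 9 county-by-time terms make 1 + 1 + 9 + 9 = 20 parameters, which already saturate those cells. The Adapted by time term equals the sum of the by-time indicators of the Adapted counties, so it is fully aliased. With county main effects only, it is estimable.

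**The case against.** The strongest reply is that the models written out in 4.3 and 4.4 contain no covariate by time term, and such terms appear only in the exploratory moderator analysis (4.8). If main effects are meant, Step 2 shows that late selection hardly touches the test. That stands, and it limits the size of the point. It does not remove it, because the plan never states the form of entry and a covariate meant to explain change has to enter by time.

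Several stronger readings are tempting but unsupported:

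- *The whole covariate set is chosen after the fact.* It is not. Strata and county are fixed, and baseline testing is barred as a selection tool.
- *Delivery mode, format and turnover will be covariates.* The Discussion commits only that the sources of variation "will be carefully considered as to whether they should be included as covariates". The pool could also yield pre-randomization factors, such as enrollment period.
- *The team will choose with outcomes by arm in hand.* The end of the trial is not the same as after unblinded analysis. Section 3.9 mentions interim outcome reports to CMHC leadership, for facilitation only, and does not say they are by arm. What is missing is a safeguard; nothing shows that the choice will be abused.
- *Step 3 gives the error rate for delivery mode in Aim 1.* It does not, because mode and format are undefined for UC-DT during the delay. Step 3 applies to a variable with a value in both arms, such as turnover, or to Adapted versus Standard.

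Including predictors of dropout is also a standard way to support a missing-at-random analysis. That stands for predictors measured at baseline.

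**Conclusion.** The point holds for the additional covariates. A stated policy leaves them open until the end, from a pool whose examples are post-randomization, without a rule, a lock or a limit to baseline variables. Under covariate by time entry and a worst-case choice, type I error goes from about 5% to roughly 7-15% for 3 to 5 covariates explaining 10-30% of change. A covariate shifted by arm by 0.2 to 0.5 SD and explaining 5-20% of change biases a null contrast by 0.04 to 0.22 SD, whether or not it was prespecified. With main effects and complete two-wave data the effect is essentially nil. These sizes rest on assumed inputs and are not predictions for this trial. The change is worth making because a fixed baseline-only set is better and costs little; sample size and stated power are unaffected.

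**What to change.** Amend 4.1 and lock it before outcomes are examined by arm:

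- **Patient models:** county dummies plus psychosis, substance use and age ≥ 50, with each of the three strata also entered by time. As main effects alone they would leave the treatment by time estimate unchanged with complete data.
- **Provider model:** county dummies only. The patient strata are not provider attributes.
- **Adapted versus Standard models:** no county by time terms, because they alias the effect under test (Step 4).
- **Post-randomization variables:** state that none enters a confirmatory model.
- **Dropout-related predictors:** allowed in the confirmatory model only if measured at baseline.
- **Delivery mode, format, turnover and other COVID-era variables:** move to a labeled set of sensitivity analyses in 4.6, which currently has three sets and none on covariates.

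The Discussion's closing statement on covariates should be aligned with this. The cost is SAP wording and three extra interaction terms in the patient models. The downside is that factors emerging late can be explored only in sensitivity analyses.

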### 3.7 Allocation

CMHCs and patients are randomized through a computerized randomization sequence. We do not stratify during randomizing at the county level. When randomizing patients, we stratify for presence of psychosis or not (current), presence of substance use or not (current) and age ( $\geq 50$  or not), as there is evidence these variables can impact sleep or treatment outcome [50, 83, 84]. Only the facilitators, assessors, and research team (i.e., not CMHCs, providers, or patients) are privy to which CMHCs and patients are allocated to which TranS-C treatment condition (Adapted versus Standard TranS-C). CMHC providers and patients know whether their patients have been randomized to receive the immediate or delayed treatment. The facilitator informs each provider when they can start having sessions. In the immediate condition, the provider is asked to begin sessions as soon as possible. In the delayed condition, the provider is asked to wait until after the patient has completed the post-delay assessment (i.e., approximately four weeks in the Adapted condition or eight weeks in the Standard condition).

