### 3.8 Sample Size

Sample size was determined via power analyses with Optimal Design [85, 86] and Stata 15 [87] and a two-sided alpha of 0.05. We used the original  $N = 8$  counties that agreed to participate, though as noted above, new counties have since been recruited to meet sample size goals determined by the following calculations. For Aims 1 and 3, 60 patients from eight randomized clusters/CMHCs was found to provide over 90% power to detect large effects (average  $d=0.89$  from [35]) between TranS-C and UC-DT, and over 80% power to detect a medium effect ( $d=0.50$ ) between Standard and Adapted TranS-C. For Aim 2, based on a prior study with a similar aim/measure [88], we expected a large effect size ( $d=0.80$ ) between Standard and Adapted TranS-C on the primary outcome of acceptability. Prior studies have reported high correlation coefficients between acceptability, feasibility, and appropriateness ( $rs=.67-.90$ ) [75, 89], thus the analysis for acceptability was expected to sufficiently power the other outcomes. Based on the site intra-class correlation (ICC) estimated from similar prior studies [90, 91], we assumed the ICC to be 0.01 and the inflation factor was calculated as  $1+(n-1)\times ICC$ . Eight clusters with an average cluster size of 10 was found to be needed to achieve over 80% power to detect a large effect for the outcome (acceptability) at the provider level. Thus, to test this aim, we would need at least 80 CMHC providers: 10 providers from 8 CMHCs (at least 4 CMHCs per randomized arm).

In sum, we aimed to randomize at least eight CMHC clinics to either Standard or Adapted TranS-C, with at least 80 providers (10 per CMHC). The goal for patients is 240 patients (30 per CMHC) randomized to immediate Standard or Adapted TranS-C and 240 randomized to UC-DT (30 per CMHC). Adding 20% to account for attrition, the total target sample size for providers is 96 and for patients is 576.

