### 4.3 Aim 1: Effectiveness Outcomes of Standard or Adapted TranS-C versus UC-DT

Multilevel modeling (MLM) [100-102] will be used to account for multiple observations nested within

patient. The level 1 equation will include dummy-coded time indicators as the predictor (0 = pretreatment, 1 = post-treatment). The level 2 equation will include dummy-coded treatment condition (0 = UC-DT, 1 = Adapted or Standard TranS-C), treatment by time interaction terms, and dummy-coded counties (0 = Alameda, 1 = Contra Costa, 2 = Kings, 3 = Monterey, 4 = Placer, 5 = Santa Cruz, 6 = Solano, 7 = Santa Clara, 8 = Santa Barbara, and 9 = Lake) as predictors. The treatment effects of interest will be significant treatment by time interactions at the 5% level on the primary outcome of sleep disturbance and the secondary outcomes of sleep-related impairment, functional impairment, and psychiatric symptoms, all modeled as continuous variables. Significant treatment by time interactions indicate that change in patient outcomes is significantly different comparing Adapted or Standard TranS-C to UC-DT. Significant interactions will be interpreted using planned contrasts (i.e., treatment effects on change from pre-treatment to post-treatment) and graphs. Additionally, the indirect effects of TranS-C relative to UC-DT on functional impairment and psychiatric symptoms through improvements in sleep disturbance and sleep-related impairment will be tested using multilevel structural equation modeling [103].

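### As sections 4.1 and 4.3 most naturally read, the stratification and county covariates do almost nothing for the Aim 1 treatment-by-time test, which is valid but less precise than a baseline-adjusted test

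*Combined protocol and SAP*

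**What the plan says.** Patients are randomised within county to immediate TranS-C or UC-DT. Section 3.7 gives the patient-level stratification: "When randomizing patients, we stratify for presence of psychosis or not (current), presence of substance use or not (current"), and age at or above 50 or not.

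Section 4.1 carries these factors into the analysis: "Covariates will include the patient variables for which we stratified (i.e., age and presence of psychosis or substance use"). It enters counties as dummy variables in all models and says that the TranS-C versus UC-DT comparison evaluates change from pre- to post-treatment. It does not say whether a covariate acts on the level of the outcome or on its change, and it names age without the cut at 50.

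Section 4.3 codes time as pre or post and lists treatment, "treatment by time interaction terms, and dummy-coded counties" as the other predictors. The effect of interest is treatment by time, for sleep disturbance (primary) and for sleep-related impairment, functional impairment (SDS) and psychiatric symptoms (DSM-5 Cross-Cutting). It lists no county-by-time or stratum-by-time term and does not repeat the stratification covariates.

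**The concern.** A covariate that is constant over time and enters as a main effect shifts a patient's pre and post scores by the same amount. The treatment-by-time term compares changes, so the shift drops out. The adjustment that section 4.1 makes on purpose then has almost no effect on the Aim 1 test.

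Two things follow. First, county may matter for change as well as level: the post visit falls at about four weeks in Adapted counties and eight in Standard counties (sections 3.4.3, 3.6.2 and 3.7), and only a by-time term can reflect that. Second, the test is a raw difference in change, which does not make the best use of the pre score. The precision lost matters most for the three secondary outcomes. No separate power calculation is given for them, and their effects could be well below the planning value, which averages results from a trial whose providers were employed, trained and supervised in an academic setting (section 1).

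**Working it through.** **Inputs from the documents.** Section 3.8: "a two-sided alpha of 0.05"; 240 patients randomised to immediate TranS-C and "240 randomized to UC-DT (30 per CMHC"); average d=0.89 for TranS-C versus UC-DT; 20% added for attrition. **Assumed, because the documents give no value:** pre-post correlation rho of 0.3, 0.5 or 0.7; equal SD at the two visits; a smaller true effect of 0.25 SD; the size of any stratum or county effect on change.

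**1. The plan's own figures.** Section 3.8 states that "60 patients from eight randomized clusters/CMHCs was found to provide over 90% power to detect large effects". With 30 per arm, d√(n/2) = 0.89 × √15 = 3.447, and Φ(3.447 − 1.960) = 93.1%, which agrees. With 240 per arm, power exceeds 99.9%. The target also reproduces: (240 + 240) × 1.2 = 576.

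**2. Cancellation with complete data.** Write y(it) = a + b·T(i) + g·t + δ·T(i)·t + c′x(i) + u(i) + e(it), with t = 0 or 1, T the treatment and x the strata and county. Then y(i1) − y(i0) = g + δ·T(i) + e(i1) − e(i0). Both c′x(i) and u(i) are gone. Mixed models fitted to one simulated data set confirm this:

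| Model | Treatment by time | SE |
|---|---|---|
| No covariates | −0.486689 | 0.101082 |
| County and strata main effects | −0.486689 | 0.101082 |
| County and strata by time | −0.464 | 0.096 |

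**3. With 20% of post scores missing** the cancellation is no longer exact. The estimate without and with main effects was −0.4497 and −0.4522 when missingness was random. It was −0.552 and −0.514 (SE 0.107 and 0.106) when missingness depended on psychosis and arm. The shifts are 0.0025 and 0.038, the larger being about a third of a standard error.

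**4. Validity.** In 3,000-replicate simulations of complete data (480 patients, 10 counties, permuted blocks within county and strata, rho 0.5) the planned model rejected a true null 4.6% to 5.0% of the time.

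**5. Baseline adjustment against change.** In score SD units with n = 240 per arm:
- change: SE = √[4(1 − rho)/n]
- post score adjusted for pre score (ANCOVA): SE = √[2(1 − rho²)/n]
- variance ratio: 2(1 − rho²) / [4(1 − rho)] = (1 + rho)/2

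Power at a true 0.25 SD, from the noncentral t with about 478 df:

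| rho | Variance ratio | SE, change | SE, ANCOVA | Power, change | Power, ANCOVA |
|---|---|---|---|---|---|
| 0.3 | 0.65 | 0.1080 | 0.0871 | 64% | 82% |
| 0.5 | 0.75 | 0.0913 | 0.0791 | 78% | 88% |
| 0.7 | 0.85 | 0.0707 | 0.0652 | 94% | 97% |

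Equivalently, 480 × 0.65 = 312, 480 × 0.75 = 360 or 480 × 0.85 = 408 baseline-adjusted patients match the precision of 480 analysed as change. At 0.89 SD the smallest ratio of effect to SE in the table is 0.89/0.1080 = 8.2, so power exceeds 99.9% under either analysis.

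**6. By-time terms alone.** With assumed stratum and county effects on change of 0.2 SD, they cut the SE by about 1% to 3%. With larger assumed effects (0.3 SD per stratum factor, ±0.2 SD by county, rho 0.5) the mean SE falls from 0.096 to 0.091, and power at 0.25 SD goes from 74% to 77%, against 88% for ANCOVA with strata and county. If the factors do not predict change, the SE is 0.091 and power 78% both ways: no gain.

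**The case against.** The strongest reply is that the planned test is sound and prespecified as change, that the documents never say the covariates are main effects only, and that the power gain comes from a different change of method. Each part has force.

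- **Form of the covariates.** Section 4.1 leaves it open and section 4.3 does not list the strata, so main effects is an inference. It is the natural one: section 4.8 writes out its treatment-by-time-by-moderator terms, whereas section 4.3 gives no by-time term for any covariate.
- **Source of the gain.** Correct. Nearly all of it comes from adjusting for the pre score; the by-time terms add little.
- **Missing data.** The plan allows for 20% attrition, uses all available data and adds variables related to dropout, so exact cancellation will not hold in practice. The movement is nevertheless small (step 3).
- **Pre score taken after allocation.** The note to Table 1 places allocation before the pre-treatment assessment. This does not favour the change score, which gives the pre score a weight of one; ANCOVA gives it a smaller weight.
- **Patients without a pre score.** ANCOVA drops them, at odds with the all-available-data principle. This stands, and is why the fix keeps the mixed model as support.

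A reader might go further and infer that the analysis ignores the stratified randomisation or wastes the baseline data. The documents do not support that. The factors are named covariates, the pre score is in the model as the time-0 response, and baseline variables are examined as moderators (section 4.8). A reader might also infer that county differences in change leak into the treatment effect whenever missingness differs between Adapted and Standard counties. Randomisation within county prevents this unless missingness differs by arm as well as by version. Even then, under assumed missingness patterns and version differences of 0.2 to 0.5 SD, the bias was about 0.01 to 0.03 SD. Finally, the documents show that the interval to the post visit differs by county; they do not show that expected change does.

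**Conclusion.** The point holds as one of precision and specification, not validity. On the natural reading of sections 4.1 and 4.3, the stratification and county terms contribute almost nothing to the Aim 1 test: nothing with complete data and little with missing post scores. The test keeps its type I error but uses a contrast whose variance is 1/0.65 to 1/0.85 times that of a baseline-adjusted one over the assumed range of rho. That could matter for the secondary outcomes if true effects are about 0.2 to 0.3 SD. It does not matter at d=0.89, so the plan's stated Aim 1 power is not in question.

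The size depends on rho, on the true effect and on how far strata and county predict change, none of which the documents give. The cancellation and the ratio (1+rho)/2 follow from the model itself, the ratio requiring equal SDs at the two visits.

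**What to change.** In section 4.3:

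1. **Sleep-related impairment, SDS and DSM-5 Cross-Cutting.** Make the single prespecified test the treatment effect on the post score, adjusted for the pre score, psychosis, substance use, age (at or above 50 or not, as randomised) and county. Keep the all-available-data mixed model, with stratum-by-time and county-by-time terms, as the supportive analysis, so that patients missing a pre score are not lost and it is clear which test takes precedence.
2. **Sleep disturbance.** Keep the mixed model as the primary test and add stratum-by-time and county-by-time terms, since the post visit is at about four or eight weeks depending on county.
3. **Wording.** State in section 4.1 that the stratification covariates enter in these forms, with age dichotomised as at randomisation.

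The cost is SAP wording. Every variable is already collected. The mixed model gains 9 county-by-time and 3 stratum-by-time parameters, 12 in all, against a planned 480 patients before the attrition allowance. The change should be settled before outcomes are compared by arm.
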